1. Number and proportion of subjects who develop an acute febrile illness (AFI) or an acute rash illness (ARI) who have evidence of acute ZIKV or DENV infection detected within 14 days of symptom onset. This endpoint will be analyzed for all subjects overall, and by dosage group, product received, and pre-vaccination flavivirus immune status.
2. Number and severity of laboratory confirmed ZIKV and DENV infections during the study, overall, by treatment group, and pre-vaccination immune status, where severity is described by:
 - Duration of symptoms
 - Grade of symptoms (mild, moderate, severe)
 - Use of concomitant medications
 - Need for hospitalization or other medical care

Laboratory confirmation will be made by AFI or ARI with either: 1) evidence of acute ZIKV and DENV infection within 14 days of symptom onset or 2) a 4-fold rise in DENV or ZIKV neutralization titers between samples collected at the last visit prior to and at the first visit following the AFI/ARI, where available.

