Table 149: Number of Laboratory Confirmed ZIKV or DENV Infections Overall and by Confirmation Method – Baseline ZIKV Seronegative Subjects

Table 150: Number of Laboratory Confirmed ZIKV or DENV Infections Overall and by Confirmation Method – Baseline ZIKV Seropositive and DENV Seropositive Subjects

Table 151: Number of Laboratory Confirmed ZIKV or DENV Infections Overall and by Confirmation Method – Baseline ZIKV Seropositive and DENV Seronegative Subjects

Table 152: Number of Laboratory Confirmed ZIKV or DENV Infections Overall and by Confirmation Method – Baseline ZIKV Seronegative and DENV Seropositive Subjects

Table 153: Number of Laboratory Confirmed ZIKV or DENV Infections Overall and by Confirmation Method – Baseline ZIKV Seronegative and DENV Seronegative Subjects

Table 154: Summary of ARI/AI Events Occurring Through 12 Months Post Final Vaccination by ZIKV or DENV Infection Status and Confirmation Method – All Subjects

[Implementation note: This table can include any subjects who did not have a baseline flavivirus status observed.]

Infection Confirmation Status	2.5 mcg ZPIV (N*=X)				5 mcg ZPIV (N*=X)				Placebo (N*=X)				All Subjects (N*=X)			
	Number of Subjects	Number of Events	% of Events	95% CI	Number of Subjects	Number of Events	% of Events	95% CI	Number of Subjects	Number of Events	% of Events	95% CI	Number of Subjects	Number of Events	% of Events	95% CI
All Events																
Positive by PCR ^a	X	X	XX	X.X, X.X	X	X	XX	X.X, X.X	X	X	XX	X.X, X.X	X	X	XX	X.X, X.X
Positive by 4-Fold Titer Rise ^b																
Any Positive Confirmation ^{a,b}																
Negative Lab Confirmation																
Events Requiring Concomitant Medication																
Positive by PCR ^a																
Positive by 4-Fold Titer Rise ^b																
Any Positive Confirmation ^{a,b}																
Negative Lab Confirmation																
Events Requiring Medical Treatment ^c																
Positive by PCR ^a																
Positive by 4-Fold Titer Rise ^b																
Any Positive Confirmation ^{a,b}																
Negative Lab Confirmation																

N* = Total number of AFI/AI events

% = number of AFI/AI events / total number of AFI/AI events (N*)

95% CI is calculated using the Clopper-Pearson methodology for a binomial distribution.

This table includes subjects who only received dose 1.

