^a PCR confirmation includes a positive PCR result for at least one of ZIKV (blood or urine) or DENV.^b 4-fold rise in either ZIKV or DENV neutralization titers after the ARI/AI illness visit compared to before the illness visit.^c Includes hospitalization or other medical care

Tables with similar format:

Table 155: **Summary of ARI/AFI Events Occurring Through 12 Months Post Final Vaccination by ZIKV or DENV Infection Status and Confirmation Method – Baseline ZIKV Seropositive Subjects**

Table 156: **Summary of ARI/AFI Events Occurring Through 12 Months Post Final Vaccination by ZIKV or DENV Infection Status and Confirmation Method – Baseline ZIKV Seronegative Subjects**

Table 157: **Summary of ARI/AFI Events Occurring Through 12 Months Post Final Vaccination by ZIKV or DENV Infection Status and Confirmation Method – Baseline ZIKV Seropositive and DENV Seropositive Subjects**

Table 158: **Summary of ARI/AFI Events Occurring Through 12 Months Post Final Vaccination by ZIKV or DENV Infection Status and Confirmation Method – Baseline ZIKV Seropositive and DENV Seronegative Subjects**

Table 159: **Summary of ARI/AFI Events Occurring Through 12 Months Post Final Vaccination by ZIKV or DENV Infection Status and Confirmation Method – Baseline ZIKV Seronegative and DENV Seropositive Subjects**

Table 160: **Summary of ARI/AFI Events Occurring Through 12 Months Post Final Vaccination by ZIKV or DENV Infection Status and Confirmation Method – Baseline ZIKV Seronegative and DENV Seronegative Subjects**

Table 161: Maximum Severity of Symptoms of AFI/ARI Events Reported Through 12 Months Post Final Vaccination by Treatment Group – All Subjects

[Implementation Note: If 100% of subject in all groups are counted in the “None” rows, then suppress the “Mild”, “Moderate”, and “Severe” columns. This table can include any subjects who did not have a baseline flavivirus status observed.]

Symptom	2.5 mcg ZPIV (N=X)				5 mcg ZPIV (N=X)				Placebo (N=X)				All Subjects (N=X)			
	None	Mild	Moderate	Severe	None	Mild	Moderate	Severe	None	Mild	Moderate	Severe	None	Mild	Moderate	Severe
	n (%)	n (%)	n (%)	n (%)	n (%)	n (%)	n (%)	n (%)	n (%)	n (%)	n (%)	n (%)	n (%)	n (%)	n (%)	n (%)
Any Symptom	xx (xx)	xx (xx)	xx (xx)	xx (xx)	xx (xx)	xx (xx)	xx (xx)	xx (xx)	xx (xx)	xx (xx)	xx (xx)	xx (xx)	xx (xx)	xx (xx)	xx (xx)	xx (xx)
Fever																
Feverishness																
Lethargy																
Restlessness																
Rash not at injection site																

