Table 168: Maximum Severity of Symptoms of AFI/ARI Events Reported Through 12 Months Post Final Vaccination by ZIKV or DENV Infection Confirmation Status and Treatment Group – All Subjects

[Implementation Note: If 100% of AFI/ARI events in all columns are counted in the “None” rows, then suppress the “Mild”, “Moderate”, and “Severe” columns. This table can include any subjects who did not have a baseline flavivirus status observed.]

Infection Confirmation Status	2.5 mcg ZPIV (N=X)				5 mcg ZPIV (N=X)				Placebo (N=X)				All Subjects (N=X)			
	None	Mild	Moderate	Severe	None	Mild	Moderate	Severe	None	Mild	Moderate	Severe	None	Mild	Moderate	Severe
	n (%)	n (%)	n (%)	n (%)	n (%)	n (%)	n (%)	n (%)	n (%)	n (%)	n (%)	n (%)	n (%)	n (%)	n (%)	n (%)
Any Symptom																
Positive by PCR ^a (N*=X)	xx (xx)	xx (xx)	xx (xx)	xx (xx)	xx (xx)	xx (xx)	xx (xx)	xx (xx)	xx (xx)	xx (xx)	xx (xx)	xx (xx)	xx (xx)	xx (xx)	xx (xx)	xx (xx)
Positive by 4-Fold Titer Rise ^b (N*=X)																
Any Positive Confirmation ^{a,b} (N*=X)																
Negative Lab Confirmation (N*=X)																
Repeat for:																
Fever																
Feverishness																
Lethargy																
Restlessness																
Rash not at injection site																
Nonpurulent conjunctivitis																
Headache																
Respiratory distress																
Retro-orbital pain																
Myalgia/Muscle pain																
Arthralgia/Joint pain																
Arthritis																
Nausea																
Abdominal pain																
Vomiting*																
Persistent vomiting*																

**Table 168: Maximum Severity of Symptoms of AFI/ARI Events Reported Through 12 Months Post Final Vaccination by ZIKV or DENV
Infection Confirmation Status and Treatment Group – All Subjects (continued)**

Infection Confirmation Status	2.5 mcg ZPIV (N=X)				5 mcg ZPIV (N=X)				Placebo (N=X)				All Subjects (N=X)			
	None	Mild	Moderate	Severe	None	Mild	Moderate	Severe	None	Mild	Moderate	Severe	None	Mild	Moderate	Severe
	n (%)	n (%)	n (%)	n (%)	n (%)	n (%)	n (%)	n (%)	n (%)	n (%)	n (%)	n (%)	n (%)	n (%)	n (%)	n (%)
Bleeding*																
N = number of subjects reporting at least one AFI/ARI																
N* = Number of subjects with ARI/AFI and specified confirmation results n = number of subjects reporting the symptom																
% = number of subjects reporting the symptom out of N*																

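### SAP Tables 154–160 divide treated confirmed infections by all febrile or rash illnesses, so the printed percentage and interval mix the confirmation rate with severity

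*SAP*

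**What the plan says.** SAP 3.2 sets exploratory endpoint 2 as "Number and severity of laboratory confirmed ZIKV and DENV infections during the study, overall, by treatment group, and pre-vaccination immune status". Its severity items are symptom duration, symptom grade, concomitant medication, and hospitalisation or other medical care. Protocol 11.4.4 likewise plans to describe severity in the laboratory-confirmed infections.

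The Table 154 shell (SAP Appendix 1) has three row blocks: *All Events*, "Events Requiring Concomitant Medication" and "Events Requiring Medical Treatment ^c". Each block has the same four rows: PCR positive, positive by 4-fold titer rise, any positive, and negative. Each column header carries a single N*, defined as "N* = Total number of AFI/AI events". (I read AFI/AI as AFI/ARI.) The one percentage formula is "number of AFI/AI events / total number of AFI/AI events (N", ending in the symbol N*. The interval note is "95% CI is calculated using the Clopper-Pearson methodology for a binomial distribution". The two treatment blocks have no denominator of their own. Tables 155–160 follow under "Tables with similar format", one for each of six baseline serostatus strata.

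Table 168, for the symptom-grade item of the same endpoint, uses a different denominator: "N* = Number of subjects with ARI/AFI and specified confirmation results".

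**The concern.** A reader looking for the severity of confirmed infections will want to know what share of them needed medication or care. In the two treatment blocks the shell prints something else: the share of all illnesses that were both confirmed and treated. That figure falls when an arm or stratum has more unrelated rashes and fevers, even if its confirmed infections are just as severe. Arms, strata, and confirmed versus negative rows are then not comparable on severity unless their confirmation rates are similar.

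No other summary table fills the gap:

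- Table 140 reports medication and medical treatment but does not split by confirmation.
- Table 147 splits by confirmation but has no treatment rows.
- Tables 168 and 182 split by confirmation but cover only symptom grade and duration.

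**Working it through.** The shell is empty, so there is no planned figure to reproduce. The check is what the stated formula yields.

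**Identity.** For one arm and one confirmation row, let N* be all AFI/ARI events, c the events with that confirmation result, and m those of the c that were treated.

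- Planned: m / N* = (c / N*) × (m / c)
- Conditional on confirmation result: m / c

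The planned figure can never exceed c / N*. If every confirmed infection needed medication, the table would print 10%, 25%, 50% or 75% when 10%, 25%, 50% or 75% of events were confirmed. If half needed it, the table would print 5%, 12.5%, 25% or 37.5%.

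**Confirmed against negative (assumed counts).** N* = 20, with 4 confirmed (3 treated) and 16 negative (8 treated).

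| Row | Planned | Conditional |
|---|---|---|
| Any positive | 3/20 = 15% | 3/4 = 75% |
| Negative | 8/20 = 40% | 8/16 = 50% |

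The order reverses. The confirmed row is smaller by a factor of 75/15 = 5, the inverse of the confirmation rate 4/20. Its Clopper-Pearson interval is 3.2% to 37.9% on 20 events and 19.4% to 99.4% on 4. The first interval does not contain 75%, because it is built around a different quantity.

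**Between arms (assumed counts).** 2.5 mcg: 12 events, 3 confirmed, 3 of those treated. 5 mcg: 15 events, 10 confirmed, 5 of those treated.

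| Arm | Planned (95% CI) | Conditional (95% CI) |
|---|---|---|
| 2.5 mcg | 3/12 = 25% (5.5–57.2) | 3/3 = 100% (29.2–100) |
| 5 mcg | 5/15 = 33.3% (11.8–61.6) | 5/10 = 50% (18.7–81.3) |

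**How readily two arms reverse.** All count combinations were enumerated with at least one confirmed event per arm, leaving out ties. The order reverses in 8.1% of combinations (5 v 5 events), 11.9% (10 v 10), 15.0% (12 v 15) and 14.3% (20 v 20). These are shares of possible tables, not probabilities.

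**A more generous reading.** If N* meant all treated events within the block, the first example would give 3/11 = 27% and 8/11 = 73%. That is still not the share of confirmed infections that needed treatment.

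**SAP 9.9 against the shells.** The text of 9.9 first describes summaries of any events, medically treated events and events requiring medication (Tables 140–144). It then assigns the same kind of summary by confirmation method to Tables 147–151, and the number of confirmed infections to Tables 154–158. In the shells, the treatment rows sit in Table 154. Table 147 has none, although it carries a footnote on hospitalisation and other care that attaches to no row. The text and the shells appear to be swapped.

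**The case against.** The best defence is that the table does what it says. Its column is labelled as a percentage of events, N* is defined underneath, and neither SAP 3.2 nor protocol 11.4.4 names a proportion or a denominator for severity. A reader might infer that the endpoint is lost or misreported. The documents do not support that. Every row prints its numbers of subjects and events, so in the first example the 4 and the 3 both stand in the same column and 3/4 can be formed by hand. Listing 13 gives treatment sought, and Listing 14 gives medication required, each with the confirmation result. With about 90 subjects enrolled, individual cases may well be few enough to read directly.

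A reader might also infer that a comparison will come out reversed. Nothing in the documents shows that, since they give no AFI/ARI or confirmation counts. With small counts, the conditional intervals would be wide in any case.

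The contrast with Table 168 is also imperfect: it counts subjects at maximum severity, while Table 154 counts events. It shows that the SAP conditions on confirmation status elsewhere for this endpoint, but not that the two displays would otherwise be directly comparable.

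These points limit the size of the problem. What stands is that the printed percentage and interval, which are the planned summary output for a descriptive endpoint, do not show the severity of confirmed infections, and no other summary table does so for these two items.

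**Conclusion.** The point holds as a matter of presentation and interpretation. In the two treatment blocks of Tables 154–160, the printed percentage is the confirmation rate times the treated share among confirmed events, and it can mislead whenever confirmation rates differ between the rows, arms or strata being compared. N* is the right denominator for the *All Events* block.

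The 5-fold understatement and the reversals rest on assumed counts and show only what is possible. The first example also assumes that every event is classed as positive or negative. The shell does not say how events without a PCR or paired-titer result enter N*. The endpoint is exploratory, protocol 11.1 describes the study as exploratory, and SAP 9.9 plans no test on these tables, so no primary or secondary result depends on the change. It is still worth making because it is nearly free.

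**What to change.** 1. Keep N* as the denominator in the *All Events* block.
2. In the medication and medical-treatment blocks of Tables 154–160, divide by the event count for the same confirmation row and arm in *All Events*. Print that denominator and compute the Clopper-Pearson interval on it.
3. Print N/A when that denominator is zero. The two-subject minimum in SAP 6.4 applies to strata and does not cover a stratum or arm with no confirmed events.
4. Align SAP 9.9 with the shells, so that the text assigns the treatment summaries by confirmation method to the tables that contain those rows, and resolve the unattached footnote in Table 147.

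The cost is footnote, shell and text wording. No new data are needed, because the denominators are already counted in the first block. The downside is wider intervals: in the first example the width goes from 37.9 − 3.2 = 34.7 percentage points to 99.4 − 19.4 = 80.0, which reflects how few confirmed infections there would be.

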6. GENERAL STATISTICAL CONSIDERATIONS

6.1. General Principles

All continuous variables will be summarized using the following descriptive statistics: n (non-missing sample size), mean, standard deviation, median, minimum and maximum, unless otherwise specified. The frequency and percentage of observed levels will be reported for all categorical measures; denominators for percentages will be defined for each analysis.

Listings will be provided for all data. Sort order will be specified on each listing shell in Appendix 3.

Summary tables will be structured with a column for each treatment group (2.5 mcg ZPIV, 5 mcg ZPIV, Placebo) and for all subjects for safety summaries.

All tables will be annotated with the total population size relevant to that table/group, including any missing observations.

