9.9. Other Safety Measures

Summary tables of acute febrile illness (AFI) and acute rash illness (ARI) events will be presented. The percentage of subjects who develop ARI or AFI will be summarized by treatment group and baseline flavivirus status. Additionally, summary tables for AFI/ARI events will be presented by baseline flavivirus status.

Summaries of subjects reporting any events, any medically treated events, and any events requiring concomitant medication, including the total number of events and the number, percentage and exact 95% Clopper-Pearson CI of subjects reporting an event, will be presented for all subjects and by baseline flavivirus immune status in [Table 140](#), [Table 141](#), [Table 142](#), [Table 143](#), and [Table 144](#). Similar summaries presented by infection confirmation method are presented in [Table 147](#), [Table 148](#), [Table 149](#), [Table 150](#) and [Table 151](#).

Summaries of laboratory confirmed ZIKV and DENV infections are also presented. ZIKV and DENV infection is presented via two methods: subjects presenting with ARI/AFI and positive Arbovirus PCR result within 14 days of symptom onset or subjects presenting with ARI/AFI and a 4-fold rise in ZIKV or DENV titers following the onset of illness compared to prior to illness. The total number of laboratory confirmed ZIKV or DENV infections are summarized by treatment group, baseline flavivirus status, and confirmation method in [Table 154](#), [Table 155](#), [Table 156](#), [Table 157](#), and [Table 158](#).

The distribution of the maximum severity of symptoms of each ARI/AFI event by baseline flavivirus status and treatment group will be presented in [Table 161](#), [Table 162](#), [Table 163](#), [Table 164](#), and [Table 165](#), as well as by infection confirmation status in [Table 168](#), [Table 169](#), [Table 170](#), [Table 171](#), and [Table 172](#). For subjects reporting at least one AFI/ARI the duration of reported symptoms will be described in [Table 175](#), [Table 176](#), [Table 177](#), [Table 178](#), [Table 179](#), and by infection confirmation status in [Table 182](#), [Table 183](#), [Table 184](#), [Table 185](#), and [Table 186](#).

Individual subject listings of AFI/ARI data will be included in [Listing 12](#) (subject information), [Listing 13](#) (medical treatment sought for ARI/AI), [Listing 14](#) (ARI/AI symptoms), [Listing 15](#) (vital signs), and [Listing 16](#) (laboratory results).

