Nonpurulent conjunctivitis																
Headache																
Respiratory distress																
Retro-orbital pain																
Myalgia/Muscle pain																
Arthralgia/Joint pain																
Arthritis																
Nausea																
Abdominal pain																
Vomiting*																
Persistent vomiting*																
Bleeding*																

Table 161: Maximum Severity of Symptoms of AFI/ARI Events Reported Through 12 Months Post Final Vaccination by Treatment Group – All Subjects

Symptom	2.5 mcg ZPIV (N=X)				5 mcg ZPIV (N=X)				Placebo (N=X)				All Subjects (N=X)			
	None	Mild	Moderate	Severe	None	Mild	Moderate	Severe	None	Mild	Moderate	Severe	None	Mild	Moderate	Severe
	n (%)	n (%)	n (%)	n (%)	n (%)	n (%)	n (%)	n (%)	n (%)	n (%)	n (%)	n (%)	n (%)	n (%)	n (%)	n (%)
N = number of subjects reporting at least one AFI/ARI n=number of subjects reporting the symptom % =percentage of subjects reporting the symptom out of the total number of subjects reporting at least one AFI/ARI If multiple AFI/ARI are reported for a subject, then the maximum severity is considered for each symptom. This table includes subjects who only received dose 1. * Reported as None/Any																

Tables with similar format:

Table 162: Maximum Severity of Symptoms of AFI/ARI Events Reported Through 12 Months Post Final Vaccination by Treatment Group – Baseline ZIKV Seropositive Subjects**Table 163: Maximum Severity of Symptoms of AFI/ARI Events Reported Through 12 Months Post Final Vaccination by Treatment Group – Baseline ZIKV Seronegative Subjects****Table 164: Maximum Severity of Symptoms of AFI/ARI Events Reported Through 12 Months Post Final Vaccination by Treatment Group – Baseline ZIKV Seropositive and DENV Seropositive Subjects****Table 165: Maximum Severity of Symptoms of AFI/ARI Events Reported Through 12 Months Post Final Vaccination by Treatment Group – Baseline ZIKV Seropositive and DENV Seronegative Subjects****Table 166: Maximum Severity of Symptoms of AFI/ARI Events Reported Through 12 Months Post Final Vaccination by Treatment Group – Baseline ZIKV Seronegative and DENV Seropositive Subjects****Table 167: Maximum Severity of Symptoms of AFI/ARI Events Reported Through 12 Months Post Final Vaccination by Treatment Group – Baseline ZIKV Seronegative and DENV Seronegative Subjects**

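### SAP Tables 168–174 give one denominator per row for all treatment columns; read literally, severity percentages within an arm do not add to 100%

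*SAP*

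**What the plan says.** Table 168 in SAP Appendix 1 has four column blocks: 2.5 mcg, 5 mcg, Placebo and All Subjects. Each block is split into None, Mild, Moderate and Severe, with n (%) in the cells. The rows within each symptom are the confirmation results: positive by PCR, positive by four-fold titer rise, any positive, and negative.

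Two sample sizes appear.

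- The column headings carry N: "N = number of subjects reporting at least one AFI/ARI". This is not the denominator.
- The row labels carry N*, as in "Negative Lab Confirmation (N*=X". The footnote reads "N* = Number of subjects with ARI/AFI and specified confirmation results", and the percentage is "number of subjects reporting the symptom out of N" (N* in the printed footnote).

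Tables 169–174 repeat the format by baseline serostatus.

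The neighbouring shells differ. Table 161, which ignores confirmation, uses "percentage of subjects reporting the symptom out of the total number of subjects reporting at least one AFI/ARI", and the only count it prints is the N at the head of each arm. Tables 154 and 182 put N* in the column heading, as in "2.5 mcg ZPIV (N*=X".

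The SAP text does not settle the matter. Section 9.9 says "The distribution of the maximum severity of symptoms of each ARI/AFI event by baseline flavivirus status and treatment group will be presented" and adds the breakdown by confirmation status, but names no denominator. Section 6.1 says "denominators for percentages will be defined for each analysis", which leaves the footnote in charge.

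**The concern.** A severity distribution by treatment group should add to 100% within each group. One N* per row cannot achieve that in every column. The count for All Subjects is the sum of the arm counts, so it equals an arm's count only when the other arms have none. Followed as laid out, the shell gives arm percentages that mix how severe the illnesses were with how many of the subjects in that row belong to the arm.

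These tables supply the symptom-grade part of exploratory endpoint 2, the severity of laboratory-confirmed ZIKV and DENV infections by treatment group and pre-vaccination immune status. Placebo is by far the smallest group, so the distortion is greatest in the comparison of vaccine with placebo.

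**Working it through.** **Inputs from the documents.** SAP Table 1 gives 2 + 43 on 5 mcg, 35 on 2.5 mcg, and 5 + 5 on placebo. The sum is 2 + 43 + 5 + 35 + 5 = 90, which reproduces the planned enrolment of about ninety (SAP section 4.3). Arm sizes are therefore 35, 45 and 10. The tables are empty shells, so there is no planned percentage to reproduce.

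**Assumptions, not in the documents.** A common proportion a of subjects in every arm falls in a given confirmation row (10% to 30%), and a common proportion s of these is severe (20% to 30%).

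**Step 1: the literal percentage.** Let c be the number of subjects in an arm with the row's result, and x the number of these in one grade. The cell is 100 × x / N*, where N* is c summed over the three arms. The four grades in an arm add to 100 × c / N*, the arm's share of the row.

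**Step 2: expected sums under the assumptions.** The attack rate cancels:

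| Arm | Share of row | Severe cell, s = 20% | Severe cell, s = 30% |
|---|---|---|---|
| 2.5 mcg | 35/90 = 38.9% | 7.8% | 11.7% |
| 5 mcg | 45/90 = 50.0% | 10.0% | 15.0% |
| Placebo | 10/90 = 11.1% | 2.2% | 3.3% |

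The ratios to placebo are 35/10 = 3.5 and 45/10 = 4.5 for every grade, at any common a and s. In whole numbers, a = 20% gives 7, 9 and 2 subjects, N* = 18, and sums of 7/18, 9/18 and 2/18.

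**Step 3: the arm's own count as denominator.** The cell becomes 100 × x / c. Its expected value is 20% in all three arms when s = 20% and 30% when s = 30%, and the four grades add to 100%.

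**Step 4: how often one trial would show it.** In 200,000 simulated trials per attack rate, with s = 30% and no vaccine effect, the literal Severe percentage on 5 mcg compared with placebo as follows:

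| Attack rate | Higher on 5 mcg | Lower on 5 mcg |
|---|---|---|
| 10% | 64% | 8% |
| 20% | 82% | 5% |
| 30% | 90% | 3% |

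The remaining trials tied. With arm-specific denominators, among trials with a case in both arms, the corresponding figures were 48% and 34%, 54% and 41%, and 52% and 45%, with a mean of about 30% in each arm.

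**Limit on Tables 169–174.** The shares there depend on how each serostatus stratum divides between arms, which the documents do not give. The ratios of 3.5 and 4.5 carry over only if serostatus is spread similarly across arms.

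**The case against.** The SAP never says that the denominator combines arms. That is inferred from the layout and the arm-free definition, and an arm-free definition alone proves little: Table 161's is arm-free too and is naturally read per column. Section 9.9 asks for a distribution by treatment group, so a programmer might well see four grades adding to 11% under placebo and query it. This shows what was probably intended. It does not change the footnote, and the shell has nowhere to print arm-level values. Table 161 escapes the problem because its count stands in the arm's own heading.

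The display also loses no information. Each subject is counted once per symptom at maximum severity, so an arm's four counts add to its correct denominator. Table 147 gives subjects per arm for the same four results, and Listing 14 gives the individual data. All grades in an arm shrink by the same factor, so the split within the arm is right. These points stand, and they limit the harm to comparing printed percentages between arms.

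A reader might infer that the tables would show more severe disease on vaccine than on placebo. The documents do not support that. It needs similar illness rates across arms, holds only in expectation, and may not appear with few cases. Placebo would equally show smaller percentages for None and Mild. With 10 placebo recipients in all, even a correct placebo percentage may rest on one or two people.

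Nor does any section name these tables as the place to look for vaccine-enhanced disease, and N* is not a count of confirmed infections only, because the lab-negative row has one too.

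**Conclusion.** The point holds as a defect in the shell. As laid out, Tables 168–174 divide every treatment column by one row-level count, and only the All Subjects column is then a valid severity distribution. Under equal illness rates and equal severity, the arm columns add in expectation to about 39%, 50% and 11%. The ratios of 3.5 and 4.5 to placebo come from arm size alone; they are not a forecast of what this trial will show. The tables are descriptive, and no test or primary endpoint depends on them. The change is worth making because the percentages are there to be compared between arms, and as written they cannot be.

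**What to change.** In Tables 168–174, define N* as the number of subjects in that treatment group (column) with AFI/ARI and the specified confirmation result. Print it for each arm in each row and use it as that column's denominator. The All Subjects column keeps the total. The four severity percentages then add to 100% within each arm for every symptom.

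Make the same correction in Table 135, where N* is also in the row label and is the stated denominator across arm columns, and in the tables that share its format. Table 136 follows it directly. The format reference for Table 138 points to Table 110, a solicited-event shell, and should be checked in the same pass. Table 135 reports new-onset chronic conditions, which are a primary endpoint, although Tables 36–42 already give that event category with N in the arm headings.

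The cost is footnote and shell wording plus the matching line of table programming. No new data are needed.
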